A critical question in the application of genomics to human health is whether healthcare costs will be needlessly amplified as a result of providing novel genetic information. To truly measure cost-effectiveness, we would need to measure specific clinical outcomes that will not be apparent over the course of the trial. However, in this exploratory study, we will perform a cost-consequences analysis over the timeframe of the trial. We will use standard methods for cost-consequence analysis.³⁰ We will aggregate the relevant costs and consequences described above and present them in table format. A cost-utility analysis will not be performed because it is unlikely that receiving genomic information will influence patient quality of life to a degree measurable using standard instruments.

After the all the 6-month follow-up visits are complete, the study staff will review each patient's medical record to collect data regarding tests, procedures, referrals, etc. that have been initiated post-results disclosure. For patients enrolled at BCH, medical records will be reviewed under the direction of [name] (co-PI of the MedSeq project and site-PI of MedSeq at BCH).

VII. Risks and Discomforts

Common Risks – Patients

Phlebotomy may cause a small amount of pain. In addition, subjects may get a temporary bruise at the collection site. Rarely, people faint when their blood is drawn. Very rarely, the vein may become red, swollen or infected.

There are no additional anticipated common risks associated with participation in this study.

Uncommon Risks - Patients

Uncommon risks may include:

- Emotional or psychological distress from learning genetic information about oneself or family members.
- Emotional or psychological distress from learning unanticipated information, such as alternate paternity or race.
- Inability to obtain insurance coverage not protected by the Genetic Information Nondiscrimination Act (GINA).
- Medical costs from tests ordered and/or additional office visits as a result from specific genetic information discovered.
- Loss of privacy.

Study personnel will take the following measures to ameliorate these uncommon risks:

- Patients enrolled in this study will undergo a detailed in-person informed consent process, which includes discussion of each of these uncommon risks and prepares the patient for the vast amount of possible results that could be discovered.
- The Genome Resource Center (GRC) staff will review all cases for situations that may impact patient safety [**see attached GRC Safety Monitoring Summary Sheet**]. The GRC will create a mechanism to provide feedback regarding miscommunication or misunderstanding of information between the physician and patient during the MedSeq Project. The GRC will write a cumulative report for the MPMC twice annually, or ASAP if the safety issue is deemed to be urgent. The IRB will be alerted of all issues identified through the GRC review in a cumulative adverse event report [**see attached AE reporting/MPMC schema**].

- The MedSeq Project Monitoring Committee (MPMC) will review cases of Serious and Non-serious Adverse Events twice per year at minimum; The PI will monitor all cases and seek action in real-time as appropriate. The IRB will be alerted of all Serious and Non-Serious Adverse Events according to our protocol **[see attached AE reporting/MPMC schema]**.
- Study personnel will take every precaution to keep the patient's personal identifiers confidential and protect each patient's privacy in all parts of MedSeq in which patient data is used.
- Optional GenomeConnect Validation Study: PatientCrossroads houses GenomeConnect on a platform called CONNECT. CONNECT is a registry system that securely stores data collected from study participants **[see GenomeConnect protocol appendix 8.1]**. PatientCrossroads will be providing MedSeq study staff with the identifying information of consented individuals, for the purposes of medical record review. No PHI will be shared with Geisinger Health Systems. Patient Crossroads is both HIPAA and FISMA compliant.
- Optional MedSeq Project Long-Term Follow-up: Surveys will be administered using REDCap. Of note, no information will be collected that is deemed, "high-risk, confidential information."

Risks – Physicians

There are no anticipated common or uncommon risks associated with participation in this study. Physicians will operate within the routine practice of medicine and adhere to professional standards. The genomic information about their patients derived as part of this study is an additional informational resource that may or may not be useful in the care of their patients; physicians are professionally expected to integrate a variety of informational sources into their practice and genomic information is no different.

Physicians may feel uncomfortable with genomic information about their patients derived from this study, but the training offered in the Physician Education Module and the availability of the Genetics Resource Center Staff will support them. The physicians may also contact the MedSeq Project Monitoring Committee directly with any concerns during their study participation.

Risks – Medical Geneticists

There are no anticipated common or uncommon risks associated with participation in this study. Medical geneticists will complete the surveys online at their own convenience, and participation is not expected to detract from standard work commitments. If necessary, the one-hour teleconference will be scheduled at a mutually convenient time.

VIII. Potential Benefits

Potential Benefits – Patients

There may be no direct benefits to participating individuals. Participants may learn genetic information about themselves or family members that is beneficial to them in terms of managing current disease, identifying risk of future disease which would allow the opportunity for surveillance and/or prevention, or identifying genetic information that provides personal utility, such as financial planning, family planning or satisfying one's curiosity about their own genetic makeup.

Potential Benefits – Physicians

There may be no direct benefits to participating physicians. Physicians may learn more about genetics and WGS as a result of participating in this study. Physicians may also benefit from a strengthened physician-patient relationship with their patients enrolled in this study.

Potential Benefits – Medical Geneticists

There may be no direct benefits to participating medical geneticists. Geneticists may learn more about how primary care physicians respond to genetic information in patient sessions, which could better inform future geneticist-physician interactions.

Potential Benefits – Society

There are several potential benefits to society. The time when WGS will be inexpensive enough to be done on the entire population is imminent. Results from this study will provide critical insight into how genomic information may be incorporated into the current practice of clinical medicine and identify areas of further study in subsequent larger randomized controlled trials examining the impact of delivering WGS information to physicians and their patients. There are speculative concerns that information derived from WGS could lead to undesirable outcomes, such as an overutilization of medical resources, vast misunderstanding among physicians and patients, or insurance discrimination. Without actually examining these potential risks within the context of a randomized clinical trial with a physician and patient support system in place, we will not be able to begin to understand the potential benefits, limitations and risks associated with the use of this technology in a clinical setting.

For the GenomeConnect portion of this study, society could benefit if it is determined that patient-entered data is accurate. This could inform the development of tools similar to GenomeConnect to add to the healthcare system as another source of reliable data. If patient-entered data is found to be inaccurate, this could also provide vital information to healthcare systems when designing tools to best incorporate genomic data with phenotypic information.

For the MedSeq Long-Term Follow-Up portion of this study, society could benefit from an improved understanding of the potential benefits, limitations and risks associated with the use of whole genome sequencing in a clinical setting, including its cost-effectiveness.

Patient Compensation

Participants will be compensated with \$125 for completion of the all the surveys that are part of this study. Additionally, participants will be compensated for each qualitative interview with \$40. Parking for study visits will be covered by the study.

Participants who are asked to come back for a full exam and work-up as part of the extension will be compensated \$50. Parking will be covered by the study.

Participants who choose to participate in the GenomeConnect validation study will receive a \$25 Amazon.com gift card. The gift card will be sent electronically to the email address used to register the participant for GenomeConnect, after the participant completes the body systems survey and the GenomeConnect MedSeq SES Survey.

Participants who choose to participate in the MedSeq Project Long-Term Follow-Up will receive a \$100 check.

Lottery for WGS

Participants who have been randomized to the comparison (WGS-) arm will have the opportunity to enter a lottery to receive WGS at the end of their study participation. Participants will be told about the lottery at their disclosure visit (visit 3) by the study staff. Following the disclosure visit with their physicians, study staff will ask participants if they would like to opt into the lottery for WGS. Study staff will remind participants that the lottery is completely voluntary. A total of three WGS will be reported through this lottery.

A drawing of those who have opted into the lottery will take place following the disclosure visit (visit 3) for the 33rd, 66th and 100th participants in the comparison (WGS-) arm. Winners of the lottery will be informed at their 6-month follow up visit (visit 5). At this time they can schedule a blood draw with the lab to be sent in for whole genome sequencing. Results will be reported through their own physician who is also a MedSeq Project enrolled physician. The GRC will be made available for any questions or concerns. If for any reason the patient's physician is unwilling or unable to report WGS results the study physician, [name], will report the WGS results to the participant at the BWH Center for Clinical Investigation or in the BWH Adult Medical Genetics Clinic. We will not survey or interview patients who received WGS as part of the lottery, however, we will apply the same data-sharing protocol as outlined above and include these patients in the medical record review. It is up to the physician's discretion to document any clinically relevant information learned as a result of this WGS report in the patient's medical record.

Physician Compensation

Physicians will be compensated for their time: Primary Care Physicians who surpassed their recruitment goal of 10 will receive a \$7,500 honorarium; recruiting PCPs who enrolled at least one participant but did not exceed their recruitment goal will receive a \$6,000 honorarium. Cardiologists will receive a \$1000 honorarium for their participation in this study.

Primary care physicians who recruit additional African/ African American participants, as part of the extension will receive an additional \$1000.

Geneticist Compensation

Medical geneticists will be compensated for their time. Each participating geneticist will receive a \$100 e-check for completing the first survey. If a one-hour teleconference is required to resolve significant disagreement on certain clinical vignettes, they will receive an additional \$100 e-check for participation.

IX. Monitoring and Quality Assurance

The PI will be responsible for monitoring the quality of the data collected as part of this study. All survey and audio-recorded data will be analyzed using the patient's study number and not their name or other identifiers. All blood samples and genome data will be analyzed using the patient's name, date of birth and gender in a CLIA-certified setting. The link containing the patient's study ID to personal identifiers will be kept in a locked filing cabinet and on a password-protected Excel spreadsheet in the MedSeq Project Manager's office. WGS and the generation of reports using WGS data will be conducted in CLIA-certified settings utilizing clinical genetics reporting standards already in

place. Patients will be monitored for levels of clinically significant depression and/or anxiety after learning the results of their Genome Report and/or Family History Review. The Genome Resource Center (GRC) staff will review all cases for situations that may impact patient safety [see attached GRC Safety Monitoring Summary Sheet]. An example of a situation that may impact patient safety is the miscommunication of personal genetic information. The GRC will create a mechanism to provide feedback regarding miscommunication or misunderstanding of information between the physician and patient during the MedSeq Project. The GRC will write a cumulative report for the MPMC twice annually, or immediately if the safety issue is deemed to be urgent. The IRB will be alerted of all issues identified through the GRC review in a cumulative adverse event report [see attached AE reporting/MPMC schema]. All cases of safety monitoring will be reviewed by the MedSeq Protocol Monitoring Committee (MPMC) twice per year at minimum. Serious Adverse Events (SAEs) will be reported immediately (within 24 hours) to the PI and within one week to the IRB and the MPMC. Non-serious Adverse Events (AEs) will be reviewed twice annually by the MPMC and reported annually to the IRB. [see attached AE reporting/MPMC schema].

Certificate of Confidentiality

An NIH Certificate of Confidentiality has been obtained for this study, which protects each patient's genomic and survey data generated by the MedSeq Project from forced disclosure.

X. References

1. Biesecker LG. Opportunities and challenges for the integration of massively parallel genomic sequencing into clinical practice: lessons from the ClinSeq project. *Genet Med.* 2012;14(4):393-398.
3. Illumina. Test process. 2012; http://www.everygenome.com/test_process/process.ilmn. Accessed May 17, 2012, 2012.
4. 23andMe. Exome 80x. 2011; <https://www.23andme.com/exome/>. Accessed May 17, 2012, 2012.
5. [name] E, Guyer M. Charting a course for genomic medicine from base pairs to bedside. *Nature.* 2011;470(7333):204-213.

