The MedSeq Project is an exploratory trial of WGS in clinical medicine. Since, in the future, genome sequence information will not be used in just one way, we have elected to explore two relatively “pure” examples of the categories described above using the protocol framework and leadership structure of a clinical trial. At the conclusion of this study, we will have helped create innovative protocols and novel outcome measures that can be applied safely in future large-scale multi-site randomized clinical trials with larger numbers of physicians from broad specialties and with more economically and ethnically diverse patients. Together with our colleagues from across the nation through the U01 consortium formed as a result of this funding, we will have invented a process of implementation and evaluation whereby the fruits of the Human Genome Project can be applied for the first time to the daily practice of medicine for the betterment of human health.

II. Specific Aims

The Specific Aims of this project are to:

1. Recruit, consent and enroll 2 study groups:
 - a. 10 primary care physicians and 100 of their healthy middle-aged patients
 - b. 10 cardiologists and 100 of their patients with cardiomyopathy.
2. Randomize each study group to receive standard of care versus standard of care plus WGS.
3. Monitor the entire protocol for subject safety.
4. Obtain WGS at 30x coverage in Illumina’s CLIA certified laboratory on 100 individuals enrolled and randomized to the WGS arms and determine coverage standards and base-calling accuracy for WGS data.
5. Generate and optimize an algorithm for interpreting WGS data covering the spectrum of human genetic variation, in terms of both previously reported and novel variants likely to influence the health of patients.
6. Create patient reports and provide an interface for communicating clinically relevant genomic information to practicing physicians.

7. Describe physicians' and patients' attitudes toward, and preferences for, the disclosure of WGS results at the start of the study.
8. Evaluate physicians' experiences with receiving and interpreting patients' genetic test results and how they communicate these results to their patients.
9. Explore how patients respond to and use WGS results by administering validated scales of psychological impact, personal utility, and behavioral responses, as well as economic and health outcomes.

The Specific Aims of the extension of this project include:

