1. Recruit and enroll an additional 10-15 self-identified, ostensibly healthy African American/African patients into the MedSeq Project.
 - a. Develop methods to tailor the current MedSeq Project sequencing, analysis, interpretation and reporting pipeline for individuals with diverse genetic backgrounds and report results in the MedSeq Project Genome Report.
 - b. Approach participating MedSeq Project primary care physicians to refer self-identified /African American patients from their practice to enroll in the MedSeq Project.
 - c. If needed for recruitment of African American/African participants approach additional primary care physicians within the Partners Health Care system and enroll them in MedSeq protocol.
2. Conduct a targeted phenotype assessment on MedSeq Project patient-participants who received a monogenic secondary finding on the MedSeq Project Genome Report with respect to the particular variant reported.
 - a. Collect data regarding the attitudes and experiences of individuals who undergo the process of a targeted phenotype assessment.

Genome Connect Validation Study

1. Offer an opportunity for the 50 enrolled primary care patients to enroll in a GenomeConnect/MedSeq validation study.
 - a. Partner with the Clinical Genome (ClinGen) Resource's patient portal GenomeConnect to validate the GenomeConnect Body Systems Survey.
 - b. Recruit MedSeq participants to join GenomeConnect and compare patient-reported phenotype data to the medical record.

The Specific Aim of the MedSeq Project Long-Term Follow-Up:

1. To evaluate the health impact and healthcare costs of integrating WGS into the care of patients who participated in a randomized controlled trial of WGS against family history analysis five years after results disclosure.

III. Subject Selection

Physicians

Primary Care Physicians

BWH Primary Care Practice Based Research Network (PBRN) approval was obtained **[see attached PBRN approval letter]**. Primary Care Physicians will be approached through noontime Primary Care conferences and the consent form **[see attached physician consent form – primary care]** will be distributed to interested physicians. [name] and the study staff will keep track of the Primary Care Physicians who decline study participation and document the reasons why **[see attached study decline log – physicians]**.

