[name], [name], and [name] will speak to the medical geneticists identified at genetics conferences and those identified using direct outreach by phone or in person. Geneticists who are interested in participating will be e-mailed a secure link to the REDCap-hosted survey. The first page of the survey will contain the informed consent form for potential participants to review. They will also have the opportunity to contact [name], [name], [name], and other project leaders about participation in this study. After reviewing the informed consent language on the survey, the geneticists will electronically provide consent for participation via the REDCap-hosted web survey. Consent records will be stored securely on the REDCap server.

Patients

Both Primary Care and Cardiology

Prospective patient participants will meet with a member of the study staff in the BWH Center for Clinical Investigation to discuss the study and review the consent form [**see attached patient consent form—primary care and –cardiology**]. The informed consent meeting will last approximately 30 minutes. Prospective participants who wish to participate will sign the consent form. Should prospective participants need additional time to decide whether or not to participate in the

study, the study staff will provide the consent form for the participant to take home and will follow-up one week later with the prospective participant to schedule a second appointment to review and sign the consent form in person. Patients who decide not to participate will not be contacted again, but reasons for decline will be documented **[see attached study decline log – patients]**. The MedSeq Project Manager will store the signed consent forms in a locked file cabinet in her office.

The study staff will randomize the patient to either receive WGS or not (Standard of Care) **[see attached randomization schema]** after the first in-person visit. All patients will be blinded to randomization status until the results disclosure session.

Recruitment in Primary Care and Cardiology will cease once each physician enrolls approximately 10 patients.

In the event of loss to follow-up or patient withdrawal, we will reinstitute recruitment procedures to meet our goals of having 100 patients randomized to receive WGS and 100 patients randomized to not receive WGS who all complete the 6-month follow-up. We plan to recruit and enroll 300 patients in order to ensure that 200 complete the full follow-up.

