Data Sharing through NCBI dbGaP: Consistent with the NHGRI goals of deriving ongoing value from large scale

sequencing studies, we plan to share both phenotypic and genotypic study data with other investigators, through the NCBI database of Genotypes and Phenotypes (dbGaP). We will use secure file transfer protocol (SFTP) to upload study meta data in the form of a data dictionary, phenotype data, and sequence read archives (SRAs) resulting from this research to dbGaP.

Provision of access: Investigators that wish to use study data on de-identified outcomes will seek access by contacting the MedSeq Project Executive Committee. Once an investigator has submitted a proposal for data access, we will consider the request using successful procedures employed by the PI in prior NHGRI-funded clinical trials. In brief, inquiries related to data sharing will be received and evaluated by the Executive Committee. Investigator proposals will be evaluated and a specific de-identified dataset containing the variables needed for that particular analysis will be shared with the applicant scientist. We will look for guidance from NHGRI, NHLBI the U01 Cooperative Agreement Consortium on whether to provide access to individual-level phenotypic study data or linked phenotype/genome data in the interest of patient privacy. If patients choose to co-enroll in the Partners Biobank, their sequencing data generated through MedSeq will be shared with the Partners Biobank.

VI. Biostatistical analysis

Given the lack of prior research in this area, and the broad number of topics of interest, the aims of the study are predominantly exploratory. This study is designed as a randomized clinical trial of WGS disclosure, but we do not have a large enough sample for statistical power to make valid cross-group comparisons. Nevertheless, we will explore differences in all domains across all study groups.

Qualitative Analyses

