[name] at Duke University will oversee the coding of audio recordings using the ENCOUNTER software system. Once the coding of the disclosure conversations is completed, the relational database will be exported to Drs. [name] and [name] for analysis.

Drs. [name] and [name] will obtain IRB approval at their own institutions separately for their role in this project.

Quantitative Analyses

A statistician will lead quantitative analyses. Descriptive statistics will be used to characterize physicians and patients in terms of demographic variables, motivations for participating in this study, and disclosure preferences. Descriptive statistics will also be used to characterize patients in terms of genetic literacy and comprehension, the psychological impact and personal utility of testing, and response to the information in the following domains: (a) communication with family and/or other health care providers, (b) changes in insurance purchasing behaviors or intentions, and (c) changes in health behaviors, health care utilization or behavioral intentions (e.g., diet, exercise). For measures where we have both baseline and follow-up survey data we will use standard pre-post analyses (e.g., paired t-tests, repeated measures analyses) to assess whether significant changes occurred in these domains following receipt of test results.

An initial step in our quantitative data analytic plan will be to determine potential differences between the two groups of respondents coming from a primary care setting and a cardiology clinic. Given that those from the primary care clinic do not have any particular underlying condition for which a genetic test is being ordered (unlike the patients with cardiomyopathy), it will be important to determine whether patients from these two groups can be pooled across analyses or should be analyzed separately. We will therefore examine whether respondents from the two clinics differ at baseline on key demographic characteristics as well as on our main outcomes of interest (e.g., disclosure preferences).

Economic Analysis of Utilization Data

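### The only inferential analysis stated for patient outcomes is pre-post change; the randomised WGS+ versus WGS- contrast, which could isolate sequencing, has no stated method

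*Combined protocol and SAP*

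**What the plan says.** Aim 2 in Section II is to "Randomize each study group to receive standard of care versus standard of care plus WGS". Aim 9 is to "Explore how patients respond to and use WGS results by administering validated scales". The long-term follow-up aim, in the same section, describes the parent study as a "randomized controlled trial of WGS against family history analysis five years after results disclosure".

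The opening of Section VI calls the aims mainly exploratory and states that "we do not have a large enough sample for statistical power to make valid cross-group comparisons". It continues: "Nevertheless, we will explore differences in all domains across all study groups".

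Quantitative Analyses in Section VI then sets out three steps:

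- descriptive statistics for physicians and patients;
- for measures with both baseline and follow-up data, "we will use standard pre-post analyses (e.g., paired t-tests, repeated measures analyses) to assess whether significant changes occurred in these domains" after test results are received;
- a baseline comparison of primary care with cardiology respondents, with no test named, to decide whether the clinics can be pooled.

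The Economic Analysis subsection asks whether genetic information will drive up healthcare costs, and says that costs and consequences will be tabulated using standard cost-consequence methods.

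**The concern.** The trial randomises patients so that the effect of adding WGS can be separated from everything else that happens to them. Under Section V, primary care patients in both arms receive a Family History Output and discuss it with their physician. Cardiology patients in both arms receive a family history review and a disclosure or re-disclosure of their targeted cardiomyopathy report. Both arms repeat the surveys at the same points. A change from baseline may reflect any of these, or simply time.

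The one inferential analysis that is stated looks at this mixed change. The contrast that would remove the shared part has no model, arm term, effect measure, interval or timepoint. At stake is how well the study informs Aim 9 and the larger randomised trials that it is meant to prepare (Section I).

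**Working it through.** **1. Is there a figure to reproduce?** No. The documents give no alpha, sidedness, effect size, SD or power. The headcount is consistent: 10 physicians x 10 patients x 2 study groups = 200. Section IV aims for 100 completers in each arm, which is 50 per arm per study group if split evenly.

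**2. What each analysis estimates.** Let S be the average change that patients would show without WGS, and W the average effect of adding WGS. Randomisation makes S the same in both arms, apart from chance.

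- Pre-post change in WGS+: S + W.
- Pre-post change in WGS-: S.
- Pre-post change with the arms pooled 1:1: S + W/2.
- WGS+ minus WGS-: (S + W) - S = W.

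Only the last line isolates W. Quantitative Analyses does not say which of the first three is meant. Its reference to receipt of test results leaves it unclear whether primary care WGS- patients, who receive the Family History Output alone, are in the test.

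**3. Does the promise to explore differences fill the gap?** Aim 1 applies the term study group to the primary care and cardiology groups, and Aim 2 randomises each of them. Section V (Physicians) speaks of matching the two arms within each study group. On that usage the sentence in Section VI refers to the clinics. The sentence before it, about a randomised trial of WGS disclosure, suggests that the arms are meant too. On either reading, no method is given.

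**4. Precision of the arm contrast (illustration).** Assumptions not in the documents: two-sided alpha 0.05, 80% power, equal allocation, complete data, no physician clustering, no multiplicity adjustment, and baseline/follow-up correlation r of 0.5 to 0.7.

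Unadjusted detectable difference, normal approximation, d = (1.960 + 0.842) x sqrt(2/n):

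- n = 50 per arm: 0.560 SD (0.566 with the t distribution);
- n = 100 per arm: 0.396 SD (0.398 with the t distribution).

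ANCOVA multiplies this by sqrt(1 - r^2), which is 0.866 at r = 0.5 and 0.714 at r = 0.7:

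- n = 50: 0.566 x 0.866 = 0.49, and 0.566 x 0.714 = 0.40 SD;
- n = 100: 0.398 x 0.866 = 0.34, and 0.398 x 0.714 = 0.28 SD.

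The 95% interval half-width with ANCOVA is 1.96 x sqrt((2/n)(1 - r^2)): 0.28-0.34 SD at n = 50 and 0.20-0.24 SD at n = 100.

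**5. Who belongs in the contrast.** Section V places all 10 to 15 extension participants in the WGS arm without randomisation. Added to 50 randomised primary care WGS+ patients, they would form 10/60 = 17% to 15/65 = 23% of that arm, with no randomised counterpart.

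**The case against.** The strongest defence is that the plan already discloses this. It calls itself exploratory, admits low power, and commits to exploring differences. The intention to compare arms is visible in Aim 2, in the long-term follow-up aim and in the matching of report release across arms. The list of pre-post methods is open, a repeated measures model can carry arm and arm-by-visit terms, and standard cost-consequence methods may compare arms. All of this stands. It limits the point to what the plan leaves unstated. It does not supply the method, and low power is a reason to report an estimate with an interval rather than a reason to rely on within-patient significance tests.

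A reader might infer more from the text than it supports:

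- **That the plan carries an inflated false-positive rate for WGS.** A paired test that detects a change shared by both arms has detected a true change. It would mislead only if that change were credited to WGS, and the plan does not do so.
- **That the arm comparison has been abandoned.** The promise to explore differences says otherwise.
- **That the enrolment allowance ("We plan to recruit and enroll 300 patients in order to ensure that 200 complete the full follow-up") implies a biased contrast.** It is a planning figure. Nothing says that the loss would fall in one arm, and equal loss with the same completer/non-completer difference in each arm cancels.
- **That physician clustering materially weakens the contrast.** The documents give no variance component for it, and the randomisation schema is an attachment that is not available here.

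**Conclusion.** The point holds in limited form. Section VI states one inferential analysis for patient outcomes. That analysis does not by itself isolate WGS, and the randomised contrast that would do so has no stated method. This is a weaker analysis than the design allows, not an error in a claim that the plan makes, and patient safety is not affected.

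The reading of the text rests on no assumption. The detectable differences do: about 0.57 SD (50 per arm) and 0.40 SD (100 per arm) unadjusted, or 0.40-0.49 and 0.28-0.34 SD with ANCOVA, all under the conditions listed in step 4 of the working. They agree with the plan's own view that small effects are out of reach, and they show that baseline adjustment gains precision from data already planned.

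**What to change.** - **Section VI, Quantitative Analyses.** For each measure with baseline and follow-up data, make the exploratory analysis the WGS+ minus WGS- difference by randomised arm. Use ANCOVA, or a mixed model with arm, visit and arm-by-visit, adjusted for baseline value and study group (or fitted within study group if the clinics are not pooled). Give 95% intervals and label the results exploratory. Report pre-post change descriptively by arm.
- **Extension participants.** Exclude those placed in the WGS arm without randomisation from this contrast, and describe them separately.
- **Measures collected only after disclosure, and utilisation and costs.** Give the same arm contrast without baseline adjustment. Keep WGS- patients who receive sequencing through the lottery (three in total) in the arm assigned, since the lottery section includes them in the record review.
- **Section VI, opening.** State that study groups covers both the randomised arms and the clinics.

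The cost is revised wording and a little more analysis work. No new data or patients are needed. The intervals will be wide, and should be presented as such.
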